- 2) Assess the preliminary impact of an alcohol-focused brief intervention on reducing alcohol consumption among a sample of hazardous drinking, PrEP-prescribed MSM.
- 3) Assess the preliminary impact of an alcohol-focused brief intervention on improving PrEP adherence and retention in PrEP-related care among a sample of hazardous drinking, PrEP-prescribed MSM.
- 4) Assess the preliminary impact of an alcohol-focused brief intervention on reducing condomless sex and STIs among a sample of hazardous drinking, PrEP-prescribed MSM.

IV. Study Design

We will conduct a pilot randomized controlled trial (RCT) of an alcohol-focused brief intervention with supplementary modules that focus on concurrent substance use and depression.

A total of 120 PrEP-prescribed MSM who are hazardous drinkers will be recruited from two medical clinics, Toronto General Hospital (TGH) and Maple Leaf Medical Clinic (MLMC), located in downtown Toronto. Participants will be randomly assigned to either the intervention condition or treatment as usual (TAU) based on a 2:1 intervention:TAU ratio. All participants will complete biological and behavioral measures at baseline and at 3- and 6-months post-baseline to assess PrEP-related behaviors, alcohol consumption, substance use, and depression. An overview of the trial design is depicted in Figure 1.

Figure 1. Pilot RCT design overview.

Eligibility Criteria

To be included in the study, participants must be (a) aged 18 years or older, (b) be a patient of TGH or MLMC, (c) be a man who identifies as a gay or bisexual, and/or a man who has sex with other men, (d) have been prescribed PrEP for at least 3 months, and (e) meet the criteria for hazardous drinking, (i.e., based on a score of ≥ 4 on the Alcohol Use Disorders Identification Test – Consumption measures (AUDIT-C))²⁰

Participants will be excluded if they do not meet all of the above-mentioned inclusion criteria.

Study Procedures and Measures

Men presenting for routine PrEP-related care at TGH and MLMC will be made aware of the study either through TGH/MLMC clinic staff members (e.g., doctors, nurses, clinic research staff) or via study information cards and/or posters (see “Recruitment Ad” attachment) at their respective clinics. Interested individuals will be referred to a CAMH research staff member. The CAMH research staff member will provide additional information about the study (see “Pre-Screening Script” attachment) and answer any questions that the individual may have.

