PrEP adherence. Adherence to PrEP will be assessed at baseline, 3-months, and 6-months using a combination of behavioral and biological assessments to evaluate the adherence-focused component of **Specific Aim 3**. The behavioral assessment will be comprised of adapted versions of two well-validated measures of adherence,^{43,44} identifying 1) the number of missed PrEP doses over the past seven days; and 2) the percent of PrEP doses taken over the past four weeks. These measures have been employed in a number of intervention trials and provide good estimates of adherence.⁴⁵ For both measures, suboptimal adherence will be defined as taking <80% of one's prescribed PrEP doses.¹¹ DBS samples obtained at baseline, 3-, and 6-months will be analyzed for quantities of PrEP components (e.g., tenofovir/emtricitabine (TFV/FTC)), using a validated liquid chromatography tandem mass spectrometry method widely used in PrEP research.^{6,9,46-55} The half-life of TFV is 15 hours and that of FTC is 10 hours⁵⁰ which will allow the quantification of recent use of PrEP with a single DBS sample. Furthermore, blood plasma has been shown to provide a good indication of PrEP use for periods ranging from 24 hours to seven days.^{50,51,54} A cut off for the concentration of ≤ 10 ng/ml (for either TFV or FTC) will be employed, as this has been shown to be indicative of inconsistent PrEP intake.^{50,51}

Retention in care. **Specific Aim 3** includes an additional focus on retention in PrEP-related care. Attendance at clinic visits that correspond with 3- and 6-month assessments, and attendance during any other regularly scheduled PrEP clinic visits during the 6-month follow-up period, will be used as an indicator of retention.

Engagement in condomless sex. In accordance with **Specific Aim 4**, condomless sex will be assessed at baseline and follow-up study visits using an adapted version of a validated MSM-focused sexual behavior assessment that queries condom use during the past three months.⁵⁶ Responses at each time point will be dichotomized to identify participants who engaged in any condomless anal sex. As an objective indicator of condomless sex, incident chlamydia, gonorrhea, syphilis, and HCV, diagnosed at each time point, will be identified through chart extraction.

Additional Measures

Participant characteristics. Demographic factors to be collected include age, race, educational background, and income. These factors will be queried during the baseline assessment.

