Substance use and Depression. Substance use other than alcohol will be assessed using the National Institute on Drug Abuse (NIDA) - Modified Assist Screening Tool (NIDA M-ASSIST).⁵⁷ This measure queries lifetime use of a variety of substances, frequency of substance use during the past three months, and negative consequences experienced as a result of substance use. Participants will be identified as possessing a potential substance use issue based on NIDA M-ASSIST scoring. Participants will complete the Center for Epidemiologic Studies Depression Scale-10 (CESD-10).⁵⁸ A score ≥ 10 will be used as an indicator of the presence of marked depressive symptomatology.⁵⁸ Both measures will be administered at baseline and at the two follow-up time points.

It should be noted that the demographic and behavioral measures (i.e. alcohol consumption, PrEP adherence, retention in care and engagement in condomless sex) included in this study were previously approved in the first phase of this study (CAMH REB# 101/2017-02; UHN REB# 18-5014).

Data Analysis

Statistical power. As this is a feasibility study and not intended as a definitive clinical trial, sample size considerations focus on expected effect sizes detectable with the design. The following effect size for the variable that likely has the least power (i.e., adherence –**Aim 3**) can be detected based on the following assumptions: there is a combined effect of 1) the suggested alcohol intervention on alcohol intake,⁵⁹ and 2) the effect of lowered alcohol intake on PrEP adherence.¹¹ Suboptimal PrEP adherence, defined as taking $<80\%$ of all doses, was estimated based on the literature¹¹ and assumed to be 30% among heavy alcohol users.⁸ With the current sample size, we would be able to significantly detect Odds Ratios of 3 and higher, and assuming confounding with an R^2 of other variables on the dependent variable, Odds Ratios of 3.5 and higher. We will be able to detect differences in proportions of about 20% with a 95% Confidence Interval between 2% and 28%.⁶⁰ Other factors in **Aims 2, 3, and 4** can detect smaller effect sizes.

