Statistical analyses. Analyses pertaining to feasibility and acceptability indicators (**Aim 1**) will be based on descriptive statistics involving frequency counts (e.g., intervention completion rates) and mean scores (i.e., acceptability measure). The anticipated patterns pertaining to **Aims 2, 3, and 4** will be tested with generalized linear mixed effect models including random intercepts for every patient,^{61,62} based on the expectation that the intervention group will have better outcomes at both follow-up time points. Mixed effect models have fewer assumptions compared to more

traditional repeated measures of analyses of variance⁶¹ with respect to missing values.^{63,64}

For the quantification of the causal impact of alcohol, we will additionally use path models, where alcohol consumption levels will be introduced into the equations, with the hypothesis that the introduction of this variable will make the differences between experimental and control groups disappear.

Reference List

1. Public Health Agency of Canada. (2015) HIV and AIDS in Canada: Surveillance Report to December 31, 2014. Ottawa: Minister of Public Works and Government Services Canada. Available at: <http://www.phac-aspc.gc.ca/aids-sida/publication/epi/2010/index-eng.php>. Accessed April 13 2017.
2. Public Health Agency of Canada. (2015) Summary: Estimates of HIV Incidence, Prevalence and Proportion Undiagnosed in Canada, 2014. Available at: <http://healthycanadians.gc.ca/publications/diseases-conditions-maladies-affections/hiv-aids-estimates-2014-vih-sida-estimations/index-eng.php>. Accessed April 13 2017.

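### The quoted 95% interval of 2% to 28% cannot belong to a 20-point difference at N=120; 30% v 10% gives about 5% to 36%

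*Combined protocol and SAP*

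**What the plan says.** Under IV. Study Design, "A total of 120 PrEP-prescribed MSM who are hazardous drinkers will be recruited" and randomised two to one in favour of the intervention, which gives 80 intervention and 40 TAU.

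The Statistical power paragraph under Data Analysis takes PrEP adherence (Aim 3) as the outcome with least power. Suboptimal adherence, meaning under 80% of doses taken, is "assumed to be 30% among heavy alcohol users". Two statements follow about what the design can show:

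- On odds ratios: "With the current sample size, we would be able to significantly detect Odds Ratios of 3 and higher", rising to 3.5 when "assuming confounding with an R^2 of other variables on the dependent variable". No value for that R² is given.
- On the difference in proportions: "We will be able to detect differences in proportions of about 20% with a 95% Confidence Interval between 2% and 28"%. Reference 60, a comparison of eleven interval methods for two independent proportions, is cited. The method used is not named.

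The paragraph states no power, no alpha, no intervention-arm rate and no allowance for loss. It opens with the caveat "As this is a feasibility study and not intended as a definitive clinical trial".

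**The concern.** The interval looks wrong on sight. Its midpoint is (2 + 28)/2 = 15, not 20, and it reaches 18 points below the estimate but only 8 above. Intervals for a difference in proportions are not exactly symmetric, but at these sample sizes they are not that lopsided.

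This is the only precision figure offered for N=120. A reader using the pilot to plan a larger trial would think it more precise than it is. The odds ratios beside it cannot serve as a check, because the power and model behind them are not given.

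**Working it through.** **Inputs.** N = 120 at 2:1, so TAU n₁ = 40 and intervention n₂ = 80 (Study Design). TAU rate p₁ = 0.30 (Statistical power). Difference d = 0.20 (same paragraph), so p₂ = 0.10; this rate is inferred, not stated. Two-sided 95%, z = 1.96. No loss, since none is stated.

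**Newcombe interval (hybrid score).** The Wilson limits for each arm are

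(p + z²/2n ± z√[p(1−p)/n + z²/4n²]) / (1 + z²/n).

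- TAU, 12/40: l₁ = 0.1807, u₁ = 0.4543.
- Intervention, 8/80: l₂ = 0.0515, u₂ = 0.1851.

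Lower limit = d − √[(p₁−l₁)² + (u₂−p₂)²] = 0.20 − √(0.1193² + 0.0851²) = 0.053.

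Upper limit = d + √[(u₁−p₁)² + (p₂−l₂)²] = 0.20 + √(0.1543² + 0.0485²) = 0.362.

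**Wald interval.** SE = √(0.30×0.70/40 + 0.10×0.90/80) = 0.0798, so 0.20 ± 1.96×0.0798 = 0.044 to 0.356.

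**Variants for a 20-point difference, 30% v 10%:**

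| Setting | 95% interval |
|---|---|
| Stated in the plan | 2% to 28% |
| Newcombe, 40/80 | 5.3% to 36.2% |
| Wald, 40/80 | 4.4% to 35.6% |
| Miettinen-Nurminen, 40/80 | 5.5% to 36.6% |
| Agresti-Caffo, 40/80 | 4.4% to 35.5% |
| Newcombe, 60/60 | 5.7% to 33.6% |
| Newcombe, 10% loss assumed (36/72) | 4.6% to 37.0% |
| Newcombe, 20% loss assumed (32/64) | 3.7% to 38.1% |

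**Does it depend on the inferred 10%?** No. Over all pairs of rates exactly 20 points apart, the smallest Newcombe upper limit is 30.0% at 40/80, in either direction, and 31.8% at 60/60. The smallest Wald upper limits are 28.8% and 30.1%. The 40/80 minima occur only at the extremes (20% v 0%, or 100% v 80%), where the lower limit is 8.6% (Newcombe) or 11.2% (Wald), not 2%.

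**Where does 2% to 28% come from?** At 40/80, the TAU v intervention counts with both Newcombe limits within one point of 2% and 28% are 7/40 v 3/80, 7/40 v 4/80, 8/40 v 5/80, 37/40 v 61/80 and 38/40 v 63/80. These are differences of 12.5 to 16.25 points, and the opposite direction gives the same range. None has a 30% rate in either arm. With 12/40 under TAU, the smallest difference whose interval excludes zero is v 11/80 (16.25 points), and its interval is already 1.2% to 32.8%.

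**The odds ratios.** The odds at 30% are 0.30/0.70 = 0.4286.

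- OR 3: 0.4286/3 = 0.1429, a rate of 12.5%, difference 17.5 points, Newcombe 2.6% to 33.9%.
- OR 3.5: 0.4286/3.5 = 0.1224, a rate of 10.9%, difference 19.1 points, Newcombe 4.3% to 35.3%.

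Neither gives an upper limit of 28%. For an unadjusted single-visit two-sided 5% test,

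power = Φ[(d − 1.96·SE₀)/SE₁],

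with SE₀ from the pooled rate and SE₁ from the separate rates:

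| Fall from 30% to | SE₀ | SE₁ | Power |
|---|---|---|---|
| 12.5% (OR 3) | 0.0749 | 0.0813 | 64% |
| 10.9% (OR 3.5) | 0.0732 | 0.0804 | 72% |
| 10% (OR 3.9) | 0.0722 | 0.0798 | 77% |
| 9.3% (OR about 4.2) | 0.0714 | 0.0794 | 80% |

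The 80% level is an assumption, since the plan states none. This does not refute OR 3. An observed 12/40 v 10/80 is significant (z = 2.34). Adherence is also measured three times ("Adherence to PrEP will be assessed at baseline, 3-months, and 6-months") and analysed with "generalized linear mixed effect models including random intercepts for every patient", which could gain power. For the mean of two follow-up visits, the variance relative to one visit depends on the within-person correlation r and on how baseline is used:

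| Baseline handling | Factor | r = 0.3 | r = 0.5 | r = 0.9 |
|---|---|---|---|---|
| Not used | (1+r)/2 | 0.65 | 0.75 | 0.95 |
| Covariate | (1+r)/2 − r² | 0.56 | 0.50 | 0.14 |
| Change from baseline | (1+r)/2 + 1 − 2r | 1.05 | 0.75 | 0.15 |

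The plan gives neither r nor the baseline handling, so no single detectable odds ratio can be derived for its model.

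**The case against.** The strongest reply is that the figures disagree but do not show which one is wrong. The scan above is for one visit, while the plan models two. Using the factor 0.65 (r = 0.3, no baseline), 30% v 15% has a Wald half-width of 16.2 × √0.65 = 13.1 points, so 15 points with an interval of 1.9% to 28.1%. On that reading the difference is the mistaken figure, not the interval. Alternatively, 28 may be a misprint for 38: the Wald interval for 50% (n=80) v 30% (n=40) is 2.1% to 37.9%. Finally, OR 3 taken upward from 30% means 56%, for which the same test has about 79% power, so 64% makes the plan look weaker than it may be.

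It is true that the source of the slip cannot be identified, but none of these readings rescues the sentence. The first needs a 15-point difference and an assumed correlation, whereas the sentence says about 20 and cites a method for independent proportions. The other two need suboptimal adherence to be higher under intervention, whereas the Statistical analyses paragraph expects the intervention group to do better. The odds-ratio remarks are mainly a request for missing assumptions; the finding rests on the interval.

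**Conclusion.** Wrong as written, and minor. A 20-point difference at N=120 cannot have a 95% interval of 2% to 28% under any pair of rates, by Newcombe or Wald, at 2:1 or 1:1. On the plan's 30% rate and 2:1 split, with an inferred 10% under intervention and no loss, it is about 5% to 36%. The stated upper limit is 36.2 − 28 = 8.2 points too low, and the stated width is 26 points against 30.8.

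The odds ratios of 3 and 3.5 are not shown to be wrong, but they cannot be verified from what is stated. The consequence is small. Only the preliminary efficacy statements for Aims 2 to 4 are touched, Aim 1 is descriptive, the study is declared not definitive, and both the stated and the recomputed interval exclude zero.

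**What to change.** Keep N=120. In the Statistical power paragraph, replace the interval sentence with:

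> Assuming 30% suboptimal adherence under TAU, with 40 TAU and 80 intervention participants, an observed 30% v 10% would have a Newcombe 95% confidence interval of about 5% to 36%.

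This holds whichever of the present figures was mistaken, because it states its own inputs. Then add:

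> An unadjusted single-visit comparison at two-sided 5% has 80% power for a fall from 30% to about 9% (21 points, odds ratio about 4.2).

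For the odds ratios, either keep 3 and 3.5 and state the power, alpha, within-person correlation, loss, baseline handling and R² value that support them, or restate them on the single-visit basis.

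The cost is wording only: no extra participants, and no change to conduct or analysis. The stated precision becomes slightly less favourable, and the authors must recover or rerun the assumptions behind the odds ratios.

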Individuals who indicate that they would like to participate will complete either a brief, self-administered tablet-based eligibility screener or an over-the-phone screener (see “Pre-Screening Questionnaire” attachment), and qualifying individuals will be offered participation and asked to provide informed written consent (see “Consent Form” attachment). Potential participants will be encouraged to take as much time as they need to review the information and only give consent when they are ready to participate. The study comprises of a baseline session, and two follow-up visits at 3- and 6- months post initial visit. Designated CAMH staff members will conduct and oversee all study procedures.

Pre-Screening

A CAMH research staff member will introduce the study to the potential participant using the pre-screening script (see “Pre-Screening Script” attachment). Individuals interested to take part in the study will complete an eligibility pre-screening questionnaire (see “Pre-Screening Questionnaire” attachment) Pre-screening will take approximately 5 minutes to complete and will be conducted over the phone or in person. Questions in the screener ask participants about their age, time on PrEP, sexual orientation, and alcohol consumption patterns.

Baseline Session

During their baseline session, participants will provide samples of dried blood spots (DBS) via finger prick (see “Dried Blood Spot Testing” below and “Dried Blood Spot” attachment) and complete a self-administered tablet-based survey. The survey, which is based on the previously-approved survey that was employed in the first phase of this project (CAMH REB# 101/2017; UHN REB#18-5014), will include measures assessing PrEP-related behaviors and other key factors including alcohol use, substance use, and depression (see “Measures” below and the “Survey” attachment). Upon completion of the survey, the tablet-based program will randomly assign participants to either the intervention condition or TAU based on a 2:1 intervention:TAU ratio. Intervention condition participants will receive a one-time, alcohol-focused brief behavioural personalized feedback intervention delivered seamlessly on the same tablet, which will also embed supplementary modules focused on substance use and depression when necessary (see “Intervention” below and the “Intervention” attachment).

Intervention

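### The Aim 2–4 mixed models give the pre-randomisation baseline no stated role, and the readings left open can cost appreciable power in an 80 v 40 trial

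*Combined protocol and SAP*

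**What the plan says.** The statistical analyses paragraph (Data Analysis) gives the Aim 2–4 model as "generalized linear mixed effect models including random intercepts for every patient", "based on the expectation that the intervention group will have better outcomes at both follow-up time points". That is the whole specification. It does not say which visits are responses, which fixed effects enter, or whether the test is an arm effect or an arm-by-time effect. Baseline could be a response, a covariate or unused.

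The data to do better are collected. The Study Design section states: "All participants will complete biological and behavioral measures at baseline and at 3- and 6-months post-baseline". The Outcome Measures section confirms a baseline assessment for alcohol consumption, PrEP adherence and condomless sex. Under Baseline Session, "Upon completion of the survey, the tablet-based program will randomly assign participants", so the survey baseline precedes allocation. Retention in care is different: it is attendance during follow-up and has no baseline value.

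**The concern.** A random intercept models the correlation between a man's repeated measurements. It does not decide how his baseline value informs the arm comparison. Three models fit the sentence in the plan:

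- **Follow-up visits only.** Baseline is not used. In a linear model with complete data, adding baseline as a response with free arm-by-visit means gives the same follow-up contrast.
- **Arm-by-time with a free baseline.** The contrast is a comparison of change scores.
- **One arm effect over all three visits.** The effect is diluted by a visit at which the true difference is zero.

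Because baseline precedes allocation, the arms' expected baseline means are equal. Adjusting for baseline, or imposing that equality, is therefore valid and more precise than all three. At stake are precision and power for most Aim 2–4 outcomes, and the part of any chance baseline difference that reaches the estimate. Leaving the contrast open also allows it to be chosen after the data are seen, among analyses whose power differs widely.

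**Working it through.** **Inputs from the documents.** "A total of 120 PrEP-prescribed MSM who are hazardous drinkers will be recruited", "based on a 2:1 intervention:TAU ratio": 80 intervention, 40 TAU. Visits are at baseline, 3 and 6 months. Suboptimal adherence is "assumed to be 30% among heavy alcohol users". The claimed detectable effect is "we would be able to significantly detect Odds Ratios of 3 and higher".

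**Assumed, because not stated.** Two-sided 5% level; within-patient correlation r of 0.3, 0.5 or 0.7, equal between all visits as a random intercept implies; no dropout; the same effect at both follow-ups; 0.4 SD for a continuous outcome.

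**The plan's own figure.** Odds of 0.30/0.70 divided by 3 give 0.143, which is a proportion of 12.5%. A comparison of 30% with 12.5% at a single visit, 40 v 80, has 63.5% power; the logistic-regression variance formula gives 73.9%. The plan states no power, so these do not show its figure to be wrong. The odds ratio of 3 is used below only as an effect size, and whether it is truly detectable is a separate matter.

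**Continuous outcome, effect averaged over two follow-ups.** The variance of the arm difference is a factor V times (1/40 + 1/80) = 0.0375:

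- follow-up only: V = (1 + r)/2
- arm-by-time (change): V = (1 + r)/2 + 1 − 2r = 1.5(1 − r)
- baseline-adjusted or equal-baseline: V = (1 + r)/2 − r² = (1 − r)(1 + 2r)/2
- one arm effect over three visits: V = (1 + 2r)/3, with the effect reduced to two-thirds

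Power is Φ(effect/√(0.0375 V) − 1.96). For example, for the adjusted analysis at r = 0.3: √(0.0375 × 0.56) = 0.145, 0.4/0.145 = 2.76, and Φ(0.80) = 78.8%.

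| Analysis | V at r = 0.3 / 0.5 / 0.7 | Power % | Loss v adjusted, points |
|---|---|---|---|
| Adjusted or equal-baseline | 0.56 / 0.50 / 0.36 | 78.8 / 83.2 / 93.1 | – |
| Follow-up only | 0.65 / 0.75 / 0.85 | 72.6 / 66.5 / 61.0 | 6.2 / 16.7 / 32.0 |
| Arm-by-time | 1.05 / 0.75 / 0.45 | 52.2 / 66.5 / 86.8 | 26.6 / 16.7 / 6.2 |
| One effect, three visits | 0.53 / 0.67 / 0.80 | 47.0 / 39.2 / 33.7 | 31.8 / 44.0 / 59.4 |

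In sample-size terms at r = 0.5 to 0.7, the ratios of V for the follow-up-only and arm-by-time analyses run from 0.45/0.36 = 1.25 to 0.85/0.36 = 2.36. That is 25% to 136% more men for the same precision.

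**Binary adherence, 30% v 12.5% at both follow-ups.** Random-intercept logistic models, 1,500 simulated trials per setting, likelihood-ratio test, latent correlation 0.3 / 0.5 / 0.7:

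| Analysis | Power % | Loss, points |
|---|---|---|
| Equal baseline | 86.6 / 87.1 / 89.5 | – |
| Follow-up only | 83.5 / 81.1 / 75.5 | 3 / 6 / 14 |
| Arm-by-time | 60.4 / 68.4 / 75.4 | 26 / 19 / 14 |

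A smaller simulation (500 trials, Wald test) gave losses inside the same range: 9 / 9 / 18 for follow-up only and 26 / 20 / 11 for arm-by-time. In that run one arm effect over three visits had 52 / 52 / 37% power against 86 / 87 / 86%, a loss of 34 / 35 / 49 points.

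**Chance imbalance.** The SD of the baseline difference is √0.0375 = 0.19 SD units, and about 30% of such trials exceed 0.2 in either direction. Given a baseline difference d, the follow-up-only estimate shifts by r·d and the change estimate by −(1 − r)·d. For d = 0.2 SD and r = 0.3 / 0.5 / 0.7, that is 0.06 / 0.10 / 0.14 SD and −0.14 / −0.10 / −0.06 SD.

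**The case against.** The strongest objection is that the plan is silent and does not choose against adjustment. The analysis sentence lists no fixed effects at all, not even treatment. The Follow Up Sessions and Alcohol consumption paragraphs say that measures are repeated to detect change over time, and the power paragraph allows for an unspecified R² of other variables. A reader might infer that adjustment has been omitted and that a definite amount of power is lost; the documents support neither. This stands, and it is why every loss above is conditional.

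A reader might also infer that the baseline data are wasted, or that imbalance passes whole into the estimate. Neither follows. An arm-by-time contrast uses baseline and, for a continuous outcome with r above 0.5, beats a follow-up-only analysis. Imbalance enters only in part, and these estimators are unbiased over randomisation.

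Three limits on the figures also stand. The plan dichotomises PEth, adherence and condomless sex, so the continuous results do not carry over to them directly. Eligibility requires an AUDIT-C score of at least 4, which truncates the baseline score and makes a high correlation less certain for that measure. For binary outcomes only the equal-baseline model was simulated, not the baseline-covariate model.

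Finally, this is described as a feasibility study, with Aims 2–4 assessing preliminary impact. That lowers the stakes. It does not remove the point, since the plan says that these aims will be tested and claims detectable effects for them.

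**Conclusion.** The point holds as an improvement available at no cost, of modest severity. The plan names a random intercept and leaves the use of baseline open, and each of the three readings set out above is less efficient than a baseline-adjusted or equal-baseline model.

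For follow-up-only and arm-by-time analyses the loss is about 6 to 32 points of power (continuous, 0.4 SD) or about 3 to 26 points (binary adherence, 30% v 12.5%). It is about 32 to 59 points for a single arm effect over three visits (continuous). These sizes rest on r between 0.3 and 0.7, complete data, equal effects at both follow-ups and a two-sided 5% test, none of which the documents state. If the investigators already intend to adjust, only the wording is missing and the loss is zero. Retention in care is outside the point.

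**What to change.** For each Aim 2–4 outcome with a baseline value, state one of two models:

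1. Baseline, 3 and 6 months as responses, with the arms' baseline means held equal: visit effects plus an arm effect at each follow-up visit, and no arm main effect.
2. The 3- and 6-month visits as responses, with the baseline value as a covariate. For PEth and drink counts, enter the baseline value as continuous even where the outcome is dichotomised.

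Either is acceptable, but the plan should choose one per outcome before the data are examined. It should also name the tested contrast, which may be visit-specific or averaged over 3 and 6 months; the stated expectation of benefit at both visits fits either. Retention in care needs its own statement without a baseline term.

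The cost is a sentence or two in the statistical analyses paragraph. No new data, visits or participants are needed.

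### With a random intercept as the only named dependence structure, the 6-month change-from-baseline test may run at about 7-10% for continuous outcomes and 5-8% for binary ones; the plan should name the contrast and a freer covariance

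*Combined protocol and SAP*

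**What the plan says.** The model for Aims 2-4 is given in one sentence under Data Analysis, Statistical analyses: "generalized linear mixed effect models including random intercepts for every patient". The hypothesis attached to it is that "the intervention group will have better outcomes at both follow-up time points". That paragraph names no random slope, residual covariance, robust variance or degrees-of-freedom method. It does not say whether baseline is an outcome row or a covariate, or which term is tested. It prefers mixed models to repeated-measures analysis of variance because of how they treat missing values.

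Under Study Design, measures are taken "at baseline and at 3- and 6-months post-baseline" and men are assigned "based on a 2:1 intervention:TAU ratio". The planned size is 120, hence 80 v 40.

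Under Outcome Measures, PEth, self-reported adherence, drug level and condomless sex are each cut into two categories. AUDIT and two drink-quantity items remain as scores or counts. Retention is attendance during follow-up.

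**The concern.** A linear model with only a random intercept has one between-patient and one residual variance. It therefore imposes a single variance and a single correlation on all pairs of visits: baseline with 3 months, 3 with 6 months, and baseline with 6 months. If visits six months apart are less alike than visits three months apart, the model uses the average correlation for every comparison. The standard error of the 6-month change is then too small and that of the 3-month change too large.

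Both follow-ups carry the efficacy hypothesis, and the Follow Up Sessions and Alcohol consumption texts speak of change over time, so the affected comparison is a natural reading of the plan. At stake is a pilot signal tilted towards 6-month findings and away from 3-month ones. The stated reason for choosing mixed models, missing data, does not address this assumption.

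**Working it through.** **No plan figure to reproduce.** The documents state no type I error, alpha, power or within-patient correlation. The power paragraph says "we would be able to significantly detect Odds Ratios of 3 and higher", with suboptimal adherence "assumed to be 30% among heavy alcohol users". That is a two-proportion statement and does not bear on the covariance.

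**Inputs.** From the documents: 80 v 40 men and three visits. Assumed: two-sided 5% level, complete data, equal covariance in both arms, equal variance at each visit, no true effect, and the correlations shown below.

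**Continuous outcome, closed form.** Write r(0,6) for the baseline to 6-month correlation and r̄ for the mean of the three pairwise correlations. With unit variance, for the arm difference in 6-month change:

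- true variance = 2(1 − r(0,6)) × (1/80 + 1/40)
- variance used by the random-intercept model = 2(1 − r̄) × (1/80 + 1/40)
- ratio k = (1 − r(0,6)) / (1 − r̄)
- type I error = 2 × [1 − Φ(1.96/√k)]

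The 3-month test uses r(0,3) in place of r(0,6). The allocation term cancels.

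Worked case, correlations 0.70, 0.49, 0.70: r̄ = 1.89/3 = 0.63. At 6 months k = 0.51/0.37 = 1.378, √k = 1.174, 1.96/1.174 = 1.669, giving 9.5%. At 3 months k = 0.30/0.37 = 0.811, giving 3.0%.

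| r(0,3), r(0,6), r(3,6) | r̄ | k at 6 months | 6-month error | 3-month error |
|---|---|---|---|---|
| 0.60, 0.60, 0.60 | 0.600 | 1.000 | 5.0% | 5.0% |
| 0.50, 0.40, 0.50 | 0.467 | 1.125 | 6.5% | 4.3% |
| 0.60, 0.50, 0.60 | 0.567 | 1.154 | 6.8% | 4.1% |
| 0.70, 0.60, 0.70 | 0.667 | 1.200 | 7.4% | 3.9% |
| 0.50, 0.25, 0.50 | 0.417 | 1.286 | 8.4% | 3.4% |
| 0.70, 0.49, 0.70 | 0.630 | 1.378 | 9.5% | 3.0% |
| 0.80, 0.64, 0.80 | 0.747 | 1.421 | 10.0% | 2.7% |
| 0.45, 0.40, 0.70 | 0.517 | 1.241 | 7.9% | 6.6% |

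The last row shows that the 3-month test is conservative only when correlation depends on spacing. If both follow-ups correlate weakly with baseline, both tests are liberal.

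**Simulation, continuous outcome** (20,000 trials per scenario). Here AR(1) means that correlation is multiplied by the same factor for each further visit.

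- 6-month change, AR(1) with adjacent correlation 0.5, 0.7, 0.8: 8.7%, 9.7%, 9.9%. Mild fading (0.7 then 0.6): 7.5%. Equal correlations: 5.1%.
- Baseline as an outcome row with arm means constrained equal there, AR(1) 0.5-0.8: 7.5-9.3%.
- Baseline as a covariate: 5.3-7.9% across the patterns tried.
- Plain 6-month arm difference, AR(1) 0.5-0.8: 5.0-5.3%.
- Joint two-degree-of-freedom arm-by-visit test, AR(1) 0.5-0.8: 5.6-5.7%.
- 6-month change with an unstructured covariance, AR(1) 0.5, 0.7, 0.8: 5.1%, 4.8%, 4.9%.

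**Simulation, binary outcome** (random-intercept logistic model, Wald tests, about 2,000 trials per scenario, Monte Carlo error about 0.5 points). The correlations are those of a latent normal variable.

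| Pattern | 6-month change, prevalence 30% | 6-month change, prevalence 50% |
|---|---|---|
| Equal, 0.6 | 4.3% | 4.5% |
| Mild, 0.7 then 0.6 | 5.4% | 5.9% |
| AR(1) 0.5 | 6.8% | 6.5% |
| AR(1) 0.7 | 6.0% | 6.7% |
| AR(1) 0.8 | 6.7% | 7.8% |

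The plain 6-month arm difference ran at 4.2-4.9% throughout. A steeper pattern (0.8, 0.55, 0.8, prevalence 45%) gave 8.0%. Patient-clustered robust standard errors with a small-sample correction gave 5.0% there, 4.5% under AR(1) 0.8 and 5.0% under equal correlations.

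**The case against.** The strongest reply is that the result depends on choices the plan does not make. Much of this stands.

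- **Wording.** The plan says that the models include random intercepts, which is not the same as only random intercepts. A reader might infer that the protocol mandates an invalid covariance; it does not. It leaves the covariance unspecified, and the figures apply only if nothing is added.
- **Contrast.** No tested term is named. If the analyst compares arms at 6 months without using baseline, the error is near 5%. What remains is that baseline is collected and the text speaks of change, so a baseline-adjusted comparison is likely, and every form of it tried shows some inflation at 6 months.
- **Outcomes.** A reader might infer that 8-9% describes all of Aims 2-4. It does not: most outcomes are dichotomised and fall in the 5-8% range, and retention has no baseline value. AUDIT may even be slightly conservative (3.8-4.6%) if its baseline is the screening score, truncated by the entry criterion. No count model was simulated for the drink items, so the continuous result carries over to them only if they are transformed and analysed as continuous.
- **Unequal spread.** A reader might add that a more variable TAU arm under 2:1 allocation makes intervals too narrow. The documents give no standard deviations to support that.
- **Purpose.** The power paragraph calls this a feasibility study rather than a definitive trial, and no decision rule rests on a p-value. This limits the consequence. It does not remove the reason to specify the test correctly, since Aims 2-4 are still tested.

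**Conclusion.** The point holds conditionally. If a random intercept is the only dependence structure and correlation fades over six months, the 6-month change-from-baseline test is liberal: about 7-10% for continuous outcomes (about 5-8% with baseline as a covariate) and about 5-8% for binary outcomes, against an assumed 5%. The 3-month change test for continuous outcomes is conservative, at about 3-4%, when correlation depends on spacing. With equal correlations there is no inflation. The fading correlations, the 5% level and complete data are all assumptions, because the documents supply none of them. The plan is under-specified here rather than demonstrably wrong, and in a pilot this counts as a cheap improvement.

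**What to change.** In the Statistical analyses paragraph:

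1. Name the arm contrast at 3 months and at 6 months, and say how baseline enters the model.
2. For AUDIT score and (transformed) drink quantities, use an unstructured 3×3 visit covariance with small-sample degrees of freedom.
3. For binary outcomes, keep the logistic mixed model and report patient-clustered robust, or cluster-bootstrap, standard errors as a check. Replacing it with generalised estimating equations is not advised: that would change the estimand from patient-specific to population-averaged, and the standard form needs a stronger missing-data assumption than the mixed model the plan chose for that reason.

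The cost is small. An unstructured covariance has six parameters against two for a random intercept, so four more, or two more if visit variances are held equal (three correlations and one variance). With 120 men and three visits, the loss of precision is negligible if the correlations are in fact equal. No data collection changes.
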